#### 6.1.1 How supplied:

##### Acalabrutinib capsules

Acalabrutinib capsules for oral administration, are supplied as opaque size 1 hard gelatin capsules, with a blue cap and yellow body, containing 100 mg acalabrutinib as the active ingredient.

The capsule also contains compendial inactive ingredients: silicified microcrystalline cellulose, which is composed of microcrystalline cellulose and colloidal silicon dioxide, partially pregelatinized starch, sodium starch glycolate, and magnesium stearate.

The capsule shell contains gelatin, titanium dioxide, yellow iron oxide, and indigotine (FD&C Blue2).

Pack Size	Contents	NDC Number
60-count bottle	Bottle containing 60 capsules 100 mg, hard gelatin capsules with yellow body and blue cap, marked in black ink with 'ACA 100 mg'	0310-0512-60

##### Acalabrutinib tablets

Acalabrutinib tablets for oral administration is supplied as an orange, oval, film-coated, and biconvex, containing 100 mg acalabrutinib as the active ingredient.

Inactive ingredients in the tablet core are low-substituted hydroxypropyl cellulose, mannitol, microcrystalline cellulose, and sodium stearyl fumarate.

The tablet coating contains copovidone ferric oxide yellow, ferric oxide red, Hypromellose, medium-chain triglycerides, polyethylene glycol 3350, purified water, and titanium dioxide.

Pack Size	Contents	NDC Number
60-count bottle	Bottle containing 60 tablets with a child-resistant closure 100 mg, orange, oval, biconvex tablet, with debossment 'ACA100' on one side and plain on the reverse	0310-3512-60

Additional information can be found at the [CALQUENCE](#) website.

**Full prescribing information for acalabrutinib capsules is available at:**  
[CALQUENCE CAPSULE prescribing information](#)

**Full prescribing information for acalabrutinib tablets is available at:**  
[CALQUENCE TABLET prescribing information](#)

#### 6.1.2 Dosage and Administration:

The recommended dose is 100 mg taken orally approximately every 12 hours until disease progression or unacceptable toxicity. Advise patients to swallow capsule or tablet whole with water. Advise patients not to open, break, dissolve, or chew the capsules or tablets. Acalabrutinib capsules and tablets may be taken without regard to food. If a dose is missed by more than 3 hours, it should be skipped, and the next dose should be taken at its regularly scheduled time. Extra capsules and tablets should not be taken to make up for the missed dose. If the drug is vomited within 3 hours of being taken, it may be re-taken at the discretion of the investigator.

Subjects should be instructed to store the drug product at home out of the reach of children.

#### 6.1.3 Storage and Stability:

Acalabrutinib capsules and tablets are packaged in white, HDPE bottles and should be stored according to the storage conditions as indicated on the label. The storage condition for acalabrutinib capsules and tablets per USPI is 20°C-25°C (68°F-77°F) with excursions permitted to 15°C-30°C (59°F-86°F)

#### Handling and Disposal:

Local requirements for disposal of hazardous drugs should be followed at each participating clinical site.

Please see UNC policy on hazardous drugs:  
<https://unchealthcare-uncmc.policystat.com/policy/4734545/latest/>

#### 6.1.4 Risk Assessments

##### **Contraindications**

No contraindications are known for acalabrutinib.

##### **Important Identified Risks**

The following summarizes the important identified risks observed with acalabrutinib in hematological cancer studies. Full details regarding the clinical safety of acalabrutinib are presented in the acalabrutinib Package Insert.

##### *Hemorrhage*

Serious hemorrhagic events, including central nervous system, respiratory, and gastrointestinal hemorrhage, have been reported in clinical trials with acalabrutinib; some of these bleeding events resulted in fatal outcomes. Grade 3 or higher bleeding events, including gastrointestinal, intracranial, and epistaxis have been reported in 2% of patients. Overall, bleeding events including bruising and petechiae of any grade occurred in approximately 50% of patients with hematological malignancies.

The mechanism for hemorrhage is not well understood. Acalabrutinib may further increase the risk of hemorrhage in patients receiving antiplatelet or anticoagulant therapies and patients should be monitored for signs of bleeding. Consider the benefit-risk of withholding acalabrutinib for 3 to 7 days pre- and post-surgery depending on the surgery and the risk of bleeding (see [Section 5.2](#)). Please note that acalabrutinib should not be held for CSF sample collection via lumbar puncture.

##### *Infection*

Serious infections (bacterial, viral or fungal), including fatal events and opportunistic infections, have been reported in clinical studies with acalabrutinib. The most frequently reported Grade 3 or 4 infection was pneumonia. Across the acalabrutinib clinical development program (including subjects treated with acalabrutinib in combination with other drugs), cases of hepatitis B virus (HBV) reactivation, aspergillosis, and progressive multifocal leukoencephalopathy (PML) have occurred.

Consider prophylaxis in subjects who are at increased risk for opportunistic infections.

Subjects with infection events should be managed according to institutional guidelines with maximal supportive care and diagnostic evaluations as clinically indicated.

#### *Cytopenias*

Treatment-emergent Grade 3 or 4 cytopenias including neutropenia, anemia, and thrombocytopenia have occurred in clinical studies with acalabrutinib. Subjects with cytopenias should be managed according to institutional guidelines with maximal supportive care and diagnostic evaluations as clinically indicated. Subjects should be closely monitored as appropriate.

#### *Second Primary Malignancies*

Events of second primary malignancies, including non-solid tumors and skin carcinomas, have been reported in clinical studies with acalabrutinib. The most frequently reported second primary malignancy was skin cancer. Advise protection from sun exposure.

Subjects should be monitored for signs and symptoms of malignancy. Subjects who develop a second primary malignancy should be managed according to institutional guidelines with diagnostic evaluations as clinically indicated, and it may be necessary for subjects to permanently discontinue study treatment. Continuation of acalabrutinib treatment should be discussed with the medical monitor.

#### *Atrial Fibrillation*

Events of atrial fibrillation/flutter have been reported in clinical studies with acalabrutinib, particularly in subjects with cardiac risk factors, hypertension, diabetes mellitus, acute infections, and a previous history of atrial fibrillation. The mechanism for atrial fibrillation is not well understood. Monitor for symptoms of atrial fibrillation and atrial flutter (e.g., palpitations, dizziness, syncope, chest pain, dyspnea) and obtain an ECG as clinically indicated. Subjects with atrial fibrillation should be managed per institutional guidelines with supportive care and diagnostic evaluations as clinically indicated.

#### **Important Potential Risks**

There is one important potential risk for acalabrutinib monotherapy. Information related to this important potential risk is presented below. Additional details regarding the clinical safety of acalabrutinib are presented in the acalabrutinib Package Insert.

#### *Hepatotoxicity*

The mechanism underlying hepatotoxicity events of non-infectious etiology is currently unknown. Following a comprehensive review of hepatotoxicity events in the acalabrutinib clinical program, there was insufficient evidence to establish an association between hepatotoxicity events and acalabrutinib due to the contribution of confounding factors, absence of clinical symptoms, and quick recovery without

treatment for patients with transaminase elevations. There is limited evidence regarding hepatotoxicity of non-infectious etiology from literature for other BTK inhibitors.

## **7.0 CLINICAL ASSESSMENTS**

### **7.1 Clinical Assessments**

Clinical assessments will be performed as outlined in the [Time and Events table](#).

#### **7.1.1 Concomitant Medications**

All concomitant medication and concurrent therapies will be documented at screening and throughout the study as summarized in the [Time and Events Table](#). Dose, route, unit frequency of administration, and indication for administration and dates of medication will be captured.

#### **7.1.2 Demographics**

Demographic information (date of birth, gender, race and ethnicity) will be recorded at the screening visit.

#### **7.1.3 Medical History**

Relevant medical history, including history of current disease, other pertinent history, and information regarding underlying diseases will be recorded at the screening visit and a focused medical history on symptoms/toxicity will be performed thereafter.

#### **7.1.4 Physical Examination**

A complete physical examination including height (at screening only), weight, ECOG performance status, and vital signs (i.e., temperature and blood pressure) will be performed by either the investigator or a sub-investigator who is a physician at the screening and Cycle 1 Day 1 visits. Vital signs may be taken by appropriately qualified personnel.

Qualified staff (MD, NP, and PA) may complete the abbreviated physical exam at all other visits.

New abnormal physical exam findings must be documented and will be followed by a physician or other qualified staff at the next scheduled visit.

#### **7.1.5 Adverse Events**

Events should be assessed per NCI-CTCAE criteria, version 5.0. Information regarding occurrence of adverse events will be captured. Duration (start and stop

dates), severity/grade, outcome, treatment and relation to study drug will be recorded in the electronic case report form (eCRF).

#### **7.1.6 Performance Status**

Performance status as defined by ECOG ([Appendix F](#)) will be assessed as outlined in the Time and Events.

#### **7.1.7 Disease Assessments**

Baseline disease assessment using MRI of brain should be obtained within 28 days prior to first dosing with acalabrutinib and then conducted at intervals as noted in the [Time and Events Table](#). CT or PET-CT imaging will be performed at screening in order to confirm no evidence of systemic involvement of lymphoma. A prior scan showing no evidence of systemic involvement may be used as long as it is without the protocol windows described in the Time and Events Table. Eye exams will be performed per standard of care in subjects with noted ocular involvement detected via ophthalmologic exam during screening.

### **7.2 Laboratory Assessments**

#### **7.2.1 Hematology**

Blood will be obtained and sent to the clinical site hematology lab for a complete blood count with white blood cell differential.

#### **7.2.2 Serum Chemistry Profile**

Blood will be obtained and sent to the clinical site chemistry lab for determination of sodium, potassium, chloride, CO2, BUN, creatinine, glucose, calcium, albumin, total protein, total bilirubin, AST, ALT, alkaline phosphatase. LDH will be measured at screening.

#### **7.2.3 Coagulation Test**

International normalized ratio (INR) or prothrombin time (PT) and activated partial thromboplastin time (aPTT) will be performed during screening to ensure eligibility criterion 4.1.9 is met.

#### **7.2.4 Pregnancy Test**

A serum pregnancy test will be obtained from female subjects who are of childbearing potential within 72 hours prior to starting study treatment.

#### **7.2.5 Hepatitis C Testing**

Subjects will be tested for Hepatitis C at screening. Subjects who are hepatitis C antibody positive must have a negative PCR result. Those who are hepatitis C PCR positive will be excluded.

#### **7.2.6 Hepatitis B Prophylaxis**

Subjects will be tested for Hepatitis B at screening. Subjects must either have hepatitis B core antibody negative OR if a subject is hepatitis B core antibody positive they must have their hepatitis B viral load checked. These subjects will be excluded if their viral load is positive. Subjects who are core antibody positive and viral load negative will be considered eligible but must receive entecavir prophylaxis.

#### **7.3 Mini-Mental State Examination**

Mental status and cognitive function will be evaluated using Mini-Mental Status Examination (MMSE) questionnaire (see [Appendix G](#) ).

#### **7.4 Correlative Studies**

##### Provision of Data to Correlative Scientists

##### **Identification and Role of the Study Coordinator as the Honest Broker**

The study coordinator will be in charge of collecting and maintaining all data points and data management. The study coordinator should have adequate training to enter, manage, and deidentify data. The study coordinator will provide a unique study number to each enrolled subject. All documentation and samples will be labeled with the unique study number. The correlative teams will only be provided this unique study ID number as opposed to any other patient identifiers. The clinical team will be the only people able to access identifiable data and the study coordinator will be a conduit to provide the de-identified data to the correlative team.

##### **Requests for a data**

Identifiable data will not be given out to any correlative investigators at any time. Multicenter and UNC correlative Investigators may ask the study coordinator for a specific data set, and the study coordinator will return a deidentified data set. This data may only be used for purposes of the study. Any use other than directly related to the study must be approved by the IRB of record. If there is a need for an investigator to access identifiable data during the study, then a new IRB application will need to be submitted from that investigator detailing the reasons needed to access that data. The study coordinator will also ensure that correlative results are not returned from the correlative team to the clinical team to dictate treatment or follow-up decisions unless this is specifically approved by the IRB of record and delineated in the clinical protocol.

#### **7.4.1 Blood Pharmacokinetic Profile of Acalabrutinib**

Standard plasma pharmacokinetic parameters of orally administered acalabrutinib will be characterized, including area under the plasma concentration versus time curve for acalabrutinib will be estimated using non-compartmental analysis.

#### **7.4.2 Cerebrospinal Fluid Uptake of Acalabrutinib**

Cerebrospinal fluid sample (3 – 4 mL) will be collected when possible after (2 +/- 1 hours) oral administration of acalabrutinib to characterize its uptake. Residual sample, if available, will be stored and may be used for future research related to the study.

#### **7.4.3 Somatic Mutations in MYD88 and CXCR4**

Tumor sample for MYD88 and CXCR4 testing will be collected prior to treatment to determine correlation of mutational status and response to treatment with acalabrutinib. Testing will only be carried out if there is sufficient tissue available. Residual sample, if available, will be stored and may be used for future research related to the study.

#### **7.4.4 Rubidium-82 Positron-Emission Tomography**

Rb PET/CT will be performed at screening, at Cycle 3 Day 1 and at Cycle 7 Day 1 in the first 5 subjects at the University of North Carolina with parenchymal brain disease who consent to this testing. We will quantify the uptake by calculating SUV variables (SUVmax and SUVave of normal brain, subcutaneous fat, lung and mediastinal blood pool) and visually assessing (using the Brain Lymphoma Rubidium Visual Scoring Scale: [Appendix H](#)) the uptake at various time points at the tumor site. We will also derive various SUV-based and visual quantitative (similar to Deauville Score) scores by comparing the SUV and visual score of the tumor to the SUV and visual scores of normal structures captured on the images, e.g. lung, subcutaneous fat and aorta.

## 8.0 EVALUATIONS AND ASSESSMENTS

### 8.1 Time and Events Table

Study Assessments	Screening 	Study treatment  (Cycle length = 28 days)						End of Treatment 	Follow Up 
		C1 D1	C1 D8	C2 D1	C3 D1	C4-7 D1	C8-n D1		
Informed consent	×								
Demographics	×								
Medical history 	×	×	×	×	×	×	×	×	
Physical exam 	×	×	×	×	×	×	×	×	
Eligibility verification	×								
ECOG performance status	×	×		×	×	×	×	×	
ECG	×								
Viral testing 	×					×	×		
Hematology 	×	×	×	×	×	×	×	×	
Serum chemistry 	×	×		×	×	×	×	×	
Coagulation tests 	×								
Pregnancy test	× 	× 			×	× 	× 	×	
MRI of brain 	×				×	× 	× 		× 
 Rb PET-CT 	×				×	× 			
CT or PET/CT 	×								
Ocular Exams 	× 	× 							
CSF sample via lumbar puncture 		×	×						
Acalabrutinib PO BID 		×							
Subject diary review		×	×	×	×	×	×	×	
Toxicity assessment 	×	×	×	×	×	×	×	×	× 
Concomitant medication review	×	×	×	×	×	×	×	×	
Plasma PK assessment 			×						

Study Assessments	Screening 	Study treatment  (Cycle length = 28 days)						End of Treatment 	Follow Up 
		C1 D1	C1 D8	C2 D1	C3 D1	C4-7 D1	C8-n D1		
Correlative tumor sample testing 		×							
MMSE 	×					×	×	×	
Survival 									×

#### Footnotes to Time and Events Table

1. All screening assessments should be completed within 28 days before initiating study therapy unless otherwise specified. If screening labs are performed within 72 hours of initiating study treatment on C1D1, they do not need to be repeated. Each scheduled visit should occur within  $\pm 3$  days of the scheduled visit while the subject is receiving study treatment. The end of treatment visit should occur 30 days ( $\pm 7$  days) after discontinuing study therapy and all ongoing AEs should be followed until resolution or the condition has stabilized with no further change expected.
2. Relevant medical history will be recorded at the screening visit. Medical history focused on symptoms / toxicity will be performed thereafter. Medical history includes the collection of clinically significant AEs.
3. A complete physical exam should be conducted at screening i.e., baseline including height (baseline only) and weight. A targeted physical exam including weight should be conducted on Day 1 of each cycle. Vital signs (blood pressure, pulse and temperature) should be obtained at each visit.
4. HBV and HCV testing will be performed during screening. Subjects who are hepatitis B core antibody positive and viral load negative at baseline must receive entecavir prophylaxis. Additionally, these subjects must be monitored for hepatitis b reactivation every before beginning every 4th cycle (Cycles 4, 8...etc.).
5. Hematology should include complete blood count with white blood cell differential.
6. Serum chemistry will include sodium, potassium, chloride, CO2, BUN, creatinine, glucose, calcium, albumin, total protein, total bilirubin, AST, ALT, alkaline phosphatase. LDH will be performed at screening only.
7. International normalized ratio (INR) or prothrombin time (PT) and activated partial thromboplastin time (aPTT) will be performed during screening to ensure eligibility criterion 4.1.9 is met.
8. Serum pregnancy test must be performed in female subjects of childbearing potential within 72 hours before initiating study treatment on day 1 of cycle 1. For subsequent cycles, a pregnancy test will be done on day 1 of odd cycles.
9. MRI of brain should be obtained at screening within 28 days prior to start of study treatment and while on treatment at C3D1 ( $\pm 7$  days), C5D1 ( $\pm 7$  days), C7D1 ( $\pm 7$  days), C10D1 ( $\pm 7$  days), C13D1 ( $\pm 7$  days), C19D1 ( $\pm 7$  days), C25D1 ( $\pm 7$  days), and then annually ( $\pm 30$  days) for up to five years, or as needed, if there are any clinical signs/symptoms of progression. Scans will be continued until disease progression. If a subject comes off treatment for any reason other than disease progression (e.g. adverse events or withdraw from treatment), then the subject will have an MRI of the brain annually ( $\pm 30$  days) for up to 2 years or until disease progression.
10. Rubidium PET-CT performed at screening, C3D1 ( $\pm 7$  days), and C7D1 ( $\pm 7$  days), in the first 5 subjects at the University of North Carolina who consent to the procedure.
11. CT or PET-CT imaging will be performed at screening in order to confirm no evidence of systemic involvement of lymphoma. A prior scan showing no evidence of systemic involvement can be utilized, as long as it is performed within 28 days of starting study drug.
12. Ocular exams will be performed during screening only if the subject has ocular symptoms or recommended per standard of care. Subjects with active ocular lymphoma will have ophthalmologic evaluation (exam or imaging) to confirm CR.

13. Cerebrospinal fluid sample (3 – 4 mL) will be collected at 2 hours (+/- 1 hour) after oral administration of acalabrutinib at Cycle 1 Day 1 and Cycle 1 Day 8. Subjects who cannot have CSF samples drawn may remain in the study.
14. Acalabrutinib treatment will continue until the subject shows signs of disease progression, unacceptable toxicity, or withdraws from the study.
15. Toxicity assessment per NCI-CTCAE criteria, v.5.0.
16. Blood samples for pharmacokinetic analysis will be collected prior to acalabrutinib dosing and at 1, 2, and 4 hours after oral administration of acalabrutinib on Day 8 of Cycle 1. It is important to collect the time of last dose at each time point.
17. Testing of tumor sample for MYD88 and CXCR4 will be collected at baseline (Cycle 1 Day 1 prior to treatment initiation). Testing will only be carried out if there is sufficient tissue available. This may be from an archival sample or a fresh biopsy collection if collected per standard of care.
18. Mini-Mental State Examination (MMSE) is performed at screening, C7D1, and then every 6 months while on the study treatment. A final MMSE will be performed at the end of treatment visit.
19. From the time subjects discontinue study treatment, they will be followed for survival every 3 months ( $\pm$ 1 month) for 5 years or until death, whichever comes first. To document survival, subjects will either be contacted directly, or their medical record will be checked.

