### 4.1 Inclusion Criteria

- 4.1.1 Willing and able to participate in all required evaluations and procedures in this study protocol, including swallowing capsules and tablets without difficulty.
- 4.1.2 Ability to understand the purpose and risks of the study and provide signed and dated informed consent and authorization to use protected health information (in accordance with national and local patient privacy regulations)..
- 4.1.3 Age  $\geq 18$  years at the time of consent.
- 4.1.4 Subject has adequate performance status as defined by [ECOG](#) of  $\leq 2$ .  
*(Note: Performance status can be assessed after administration of corticosteroids.)*
- 4.1.5 Subject has histological confirmation of biopsy-proven CNS lymphoma OR MRI findings consistent with CNS lymphoma if biopsy is not possible (due to inaccessible location). Subjects with intra-ocular lymphoma will not be excluded as long as there is also parenchymal disease.
- 4.1.6 Subject has B-cell Non-Hodgkin Lymphoma.
- 4.1.7 Subject has no evidence of systemic involvement of lymphoma confirmed by CT or PET-CT imaging within 28 days prior to first dosing in the study.
- 4.1.8 Subject must have received at least one prior line of chemotherapy for primary or secondary CNS lymphoma. There is no limit on the number of prior treatment regimens.
- 4.1.9 Subject has adequate organ function as demonstrated by:

System	Laboratory Value
Hematological*	
Absolute Neutrophil Count (ANC)	$\geq 1 \times 10^9/\text{L}$
Platelets	$\geq 75 \times 10^9/\text{L}$
Renal*	
Calculated creatinine clearance	$\geq 30 \text{ mL/min}$ using the Cockcroft-Gault formula ( Appendix B )

Hepatic*	
Bilirubin	$\leq 1.5 \times$ upper limit of normal (ULN). Subjects with Gilbert's syndrome may be enrolled despite a total bilirubin level $>1.5$ mg/dL if their conjugated bilirubin is $<1.5 \times$ ULN)
Aspartate aminotransferase (AST)	$\leq 2.5 \times$ ULN
Alanine aminotransferase (ALT)	$\leq 2.5 \times$ ULN
Coagulation*	
International Normalized Ratio (INR) or Prothrombin Time (PT) and Activated Partial Thromboplastin Time (aPTT)	$\leq 2 \times$ ULN (in the absence of lupus anticoagulant)

**4.1.10** Subjects with a prior or concurrent malignancy whose natural history or treatment does not have the potential to interfere with the safety or efficacy assessment of the treatment are eligible for this trial.

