## 4.2 Exclusion Criteria

Subjects meeting any of the following exclusion criteria will *not* be able to participate in this study

- 4.2.1** Prior cancer treatment that was completed less than 14 days prior to Day 1 of study dosing or if subject has not recovered from all reversible acute toxic effects of the regimen to grade  $\leq 1$  or baseline.
- 4.2.2** Prior brain radiotherapy under the following conditions:
- Whole-brain radiotherapy (WBRT) that was completed less than 28 days prior to Day 1 of study dosing
  - Stereotactic radiosurgery (SRS) that was completed less than 14 days prior to Day 1 of study dosing.
- 4.2.3** Currently receiving or has received an investigational agent within 28 days of first dosing with study treatment. Subjects should not currently be receiving investigational treatment or have received an investigational agent within 28 days of dosing.
- 4.2.4** Subject is pregnant or breastfeeding (*Note*: breast milk cannot be stored for future use while the mother is being treated on study).
- 4.2.5** Subject has active CSF involvement that requires ongoing intrathecal chemotherapy.
- 4.2.6** Previous exposure to a BTK inhibitor.
- 4.2.7** Subjects with severe hepatic insufficiency, as defined by [Child-Pugh Score](#)  $> 6$  ([Appendix C](#)).
- 4.2.8** Subject is receiving prohibited medications or treatments as listed in [Section 5.3](#) of the protocol that cannot be discontinued/replaced by an alternative therapy. Subject requires treatment with a strong cytochrome P450 3A4 (CYP3A4) inhibitor/inducer (please consult [Section 5.3](#)). Subjects may be eligible if they are medically able to discontinue CYP3A4 inhibitors/inducers at least 14 days before the first dose of study treatment.
- 4.2.9** Subject requires or receiving anticoagulation with warfarin or equivalent vitamin K antagonists (e.g., phenprocoumon) within 14 days of first dose of study drug. Subjects requires or is taking direct oral anticoagulants (e.g. apixaban, rivaroxaban, edoxaban, lovenox) within 7 days of first dose of study drug.
- 4.2.10** Subjects receiving capsule form of acalabrutinib may not be taking proton pump inhibitors (e.g., omeprazole, esomeprazole, lansoprazole, dextansoprazole, rabeprazole, or pantoprazole). Subjects receiving proton pump inhibitors who

switch to H2-receptor antagonists or antacids and subjects receiving tablet form of acalabrutinib are eligible for enrollment to this study.

[figure not shown]

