**Table 3. Anatomic and Radiographic Endpoint Definitions**

Endpoint Definitions			
Endpoint	Response Category	Definition	Point of Measurement
Overall survival	All patients	Death as a result of any cause	Entry onto trial
Event-free survival	All patients	Failure or death as a result of any cause	Entry onto trial
Progression-free survival	All patients	Disease progression or death as a result of PCNSL	Entry onto trial
Disease-free survival	CR, CRu	Time to relapse	First documentation of response
Response duration	CR, CRu, PR	Time to relapse or progression	First documentation of response

*CR requires the following:*

(1) Complete disappearance of all enhancing abnormalities on gadolinium-enhanced MRI.

(2) No evidence of active ocular lymphoma as defined by absence of cells in the vitreous and resolution of any previously documented retinal or optic nerve infiltrates. Chronic changes of the retinal pigment epithelium in the setting of a prior retinal or optic nerve infiltrate does not preclude the definition of a CR. All patients with initial involvement of the eyes on baseline evaluation should have a detailed follow-up evaluation including dilated fundus examination and color photographs of the posterior pole of the eye. Repeat ophthalmologic evaluation is not required for patients without evidence of ocular lymphoma at baseline or interval development of ocular symptoms.

(3) At the time a CR is determined, the patient should have discontinued use of all corticosteroids for at least 2 weeks. Rare exceptions may be made for those patients receiving corticosteroids for another diagnosis (e.g., panhypopituitarism).

*CR/unconfirmed (CRu) includes those patients who fulfill the criteria for CR with the following features/limitations:*

(1) Any patient who fulfills all criteria for CR but continues to require corticosteroid therapy at any dose should be considered an unconfirmed CR. This is critical because corticosteroids may be oncolytic in treating occult tumor. In addition, corticosteroids may decrease gadolinium enhancement on MRI.

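### The baseline MRI can predate the end of the last systemic treatment or stereotactic radiosurgery, so shrinkage from that treatment can be scored as response to acalabrutinib

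*Combined protocol and SAP*

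**What the plan says.** **Baseline scan.** Footnote 9 to the Time and Events Table (8.1) reads "MRI of brain should be obtained at screening within 28 days prior to start of study treatment". Section 7.1.7 reads "Baseline disease assessment using MRI of brain should be obtained within 28 days prior to first dosing with acalabrutinib". Neither mentions the date on which earlier therapy ended.

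**Washouts.** Section 4.2.1 excludes "Prior cancer treatment that was completed less than 14 days prior to Day 1 of study dosing", and 4.2.2 excludes "Stereotactic radiosurgery (SRS) that was completed less than 14 days prior to Day 1 of study dosing". Ending 14 or more days before Day 1 is therefore allowed. Two washouts are longer: "Whole-brain radiotherapy (WBRT) that was completed less than 28 days prior to Day 1 of study dosing" (4.2.2) and "Currently receiving or has received an investigational agent within 28 days of first dosing with study treatment" (4.2.3).

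**Endpoint.** Section 3.1 counts PR plus CR at 2 months, and footnote 9 schedules the first on-treatment MRI at C3D1. Under 8.4.1, PR needs at least a 50% reduction relative to the baseline image. CR needs all enhancement to have disappeared, plus ocular and corticosteroid conditions.

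**Disease at entry.** Section 4.1.5 accepts biopsy-proven CNS lymphoma, with no date for the biopsy, or "MRI findings consistent with CNS lymphoma if biopsy is not possible (due to inaccessible location". Parenchymal disease is demanded only of subjects with intra-ocular lymphoma. No criterion asks for an enhancing lesion on the baseline scan.

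**Decision rule.** Sections 10.1 and 10.2 test ORR of 50% or less against 70% or more. The null is rejected with 10 or more responders among 15, with stated power of 72% and one-sided type 1 error of 0.15.

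**The concern.** In a single-arm trial, each subject's baseline scan is the only comparator for response. If SRS or chemotherapy is given after that scan, the change seen at C3D1 mixes its effect with that of acalabrutinib. Section 8.4.1 cannot separate the two: the reduction is measured from the baseline image and counted. Any such case adds to the responder count that decides the trial. With 15 subjects and a type 1 error already set at 0.15, one or two cases are enough to matter.

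A smaller, related gap is that the plan does not say how to classify a subject who has no enhancing lesion at baseline. PR is impossible for that subject, and the MRI part of CR is open to interpretation.

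**Working it through.** **1. Timing.** Day −n means n days before Day 1. The gap is the earliest permitted MRI day set against the latest permitted end of treatment.

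| Prior treatment | Latest permitted end | Earliest permitted MRI | MRI can precede end by |
|---|---|---|---|
| Systemic cancer treatment (4.2.1) | Day −14 | Day −28 | 28 − 14 = 14 days |
| SRS (4.2.2) | Day −14 | Day −28 | 28 − 14 = 14 days |
| Whole-brain radiotherapy (4.2.2) | Day −28 | Day −28 | 28 − 28 = 0 days |
| Investigational agent (4.2.3) | Day −28 | Day −28 | 28 − 28 = 0 days |

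Example: MRI on Day −28, SRS on Day −15, first dose on Day 1. The MRI is within 28 days, and SRS ended at least 14 days earlier. Section 4.2.11 excludes only subjects currently on chemotherapy or anticancer immunotherapy, so it does not apply. No timing criterion is breached. The last two rows leave no gap, apart from a possible tie on the boundary day.

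**2. The plan's own figures.** With X ~ Binomial(15, p):

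- Type 1 error: P(X ≥ 10 | p = 0.5) = 4944/32768 = 0.1509, which rounds to the stated 0.15.
- Power: P(X ≥ 10 | p = 0.7) = 0.7216, the stated 72%.

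Both reproduce.

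**3. Illustration of size.** Assume k of the 15 respond whatever the drug does, and the other 15 − k have a true ORR of 50%. The documents give no value for k, so the range is an assumption.

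- Chance of passing = P(Y ≥ 10 − k), with Y ~ Binomial(15 − k, 0.5).
- Expected ORR = [k + 0.5(15 − k)]/15 = 0.5 + 0.5k/15.

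| k | Chance of 10 or more responders | Expected ORR |
|---|---|---|
| 0 | 4944/32768 = 0.151 | 50.0% |
| 1 | 3473/16384 = 0.212 | 53.3% |
| 2 | 2380/8192 = 0.291 | 56.7% |
| 3 | 1586/4096 = 0.387 | 60.0% |

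Each such subject adds 0.5/15 = 3.3 points to expected ORR, because that subject would have had a 50% chance of responding anyway. A shift of 1/15 = 6.7 points per subject applies only when someone who would definitely not have responded is scored as a responder.

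**4. Subjects without a baseline lesion.** Under 8.4.1 a subject is evaluable after one cycle, with no lesion condition. PR needs a lesion to shrink. The MRI item for CR speaks of enhancement disappearing, which presupposes that some was there. The text therefore supports at least two classifications, CR or non-response, and they move ORR in opposite directions.

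**The case against.** The strongest defence is that the sequence is unlikely in practice. The MRI is to be done at screening. Footnote 11 and 7.1.7 expressly allow an earlier CT or PET-CT to be reused, and no such allowance is written for the MRI. The subject would thus have a screening MRI, receive SRS or chemotherapy, finish by Day −14 and recover from its toxicity as 4.2.1 requires. Section 4.2.11 bars current chemotherapy, and 11.3 requires eligibility to be maintained from registration to the start of treatment. If the scan itself showed progression on the earlier therapy, carry-over shrinkage is also less likely. All of this makes the case uncommon. None of it fixes the order of scan and treatment, and 4.2.11 does not name SRS.

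A reader might infer more than the text supports:

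- **That all prior therapy is exposed.** It is not. Whole-brain radiotherapy and investigational agents have washouts equal to the MRI window.
- **That a subject with no lesion is automatically a CR.** This is only one reading. The population is described throughout as relapsed or relapsed/refractory. Subjects entered on MRI findings, or with ocular plus parenchymal disease, would normally have a lesion. The open route is mainly biopsy-proven disease that is leptomeningeal, resected or already responding, and such a subject could equally count as a non-responder.
- **That eligibility must require a measurable enhancing brain lesion.** This is a debatable trade-off. It would exclude leptomeningeal-only disease, which section 1.2 includes in its disease description, from a trial already reduced to a pilot because its accrual goal was not feasible.
- **That the PR definition mishandles corticosteroids.** Section 8.4.1 does observe that "corticosteroids may decrease gadolinium enhancement on MRI", but it uses this to downgrade a CR on steroids to unconfirmed. Ignoring dose for PR is part of the adopted criteria, and 4.2.11 expects steroids to be tapered. A supportive analysis is reasonable, but changing the definition is not called for.

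**Conclusion.** The point holds for systemic therapy and SRS. The baseline scan may precede the end of the last treatment by up to about 14 days, and the plan then credits any resulting shrinkage to acalabrutinib. The stated power and type 1 error are correct as binomial calculations; the weakness lies in attributing the response.

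The size is conditional. One or two subjects who respond whatever the drug does would raise the chance of passing at a true 50% from 0.151 to 0.212 or 0.291, and expected ORR by 3.3 points each. This assumes certain response in those subjects and 50% in the rest. The true number may be zero. The point should be fixed because the remedy is cheap and one case is influential; it does not invalidate the design.

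**What to change.** 1. **Footnote 9 and 7.1.7:** require the baseline MRI to be within 28 days before Day 1 and after the last dose or fraction of any prior anti-lymphoma treatment. No washout or eligibility rule changes.
2. **Subjects already enrolled:** compare the baseline MRI date with the last-treatment date, and report ORR with any affected responder counted as a non-responder, alongside the planned analysis.
3. **Section 10.3:** state that a subject with no enhancing lesion on the baseline MRI cannot be counted as a CR on MRI grounds alone. This takes the place of a measurable-lesion eligibility criterion.
4. **Optional and supportive:** a sensitivity ORR that counts a PR as non-response when the recorded corticosteroid dose at C3D1 exceeds that at the baseline MRI. The adopted PR definition stays unchanged. Concomitant-medication doses and dates are already collected under 7.1.1.

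The cost is amendment wording, an occasional later or repeated screening MRI, and a little extra analysis.
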